#### 6.1.2 Response rate

Antibody responder is defined as the study subject whose serum antibody titer is greater than the response threshold (see section 9.2.2 for definition) at any visit after baseline. Response rate will be calculated as the percent of the number of antibody responders versus the total number of subjects for each arm.

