#### 6.1.1 Anti-A $\beta$ antibody measurement

For the immunogenicity assessment of the investigational product, UB-311, the level of anti-A $\beta$  antibodies in the serum samples will be measured by a validated enzyme immunoassay manufactured by United Biomedical, Inc. (UBI).

The level of anti-A $\beta$  antibodies is assessed at every visit throughout the study period from V1 to V13 (Weeks 0/baseline, 4, 12, 16, 24, 28, 36, 40, 48, 52, 60, 64, and 78). For visits that UB-311 or placebo is scheduled to be administrated (V1, V2, V3, V5, V7, V9, and V11), blood samples will be collected before the treatment.

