### 9.2.2 Immunogenicity variables

The level of anti-A $\beta$  antibodies is one of the primary endpoints and is assessed at baseline (V1) and every following visit (V2 to V13). The one-sided 95% confidence interval (CI, right side) from all visits (V1 to V13) for subjects in Arm 3 (placebo group) will be calculated as the threshold of response. Antibody responders will be defined as the subjects with serum antibody titer > response threshold at any visit after baseline. Response rate will be calculated for each arm.

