5.9 Analysis of Immunogenicity Variable

Anti-A β antibodies will be summarized by presenting summary statistics of raw data and change from baseline values (n, mean, standard deviation, median, range) at each scheduled visit in mITT Population and PP Population.

The Kruskal-Wallis test or analysis of variance (ANOVA) for continuous variables for baseline information will be performed for comparing the un-adjusted change among Arm 1, Arm 2 and Arm 3.

A repeated-measures mixed-effects model with treatment (Arm 1+ Arm 2 vs. Arm 3, Arm 1 vs. Arm 3 and, Arm 2 vs. Arm 3), study visit, time-by-treatment, APOE4 status, and baseline as a

covariate will be used to analyze change from baseline of anti-A β antibodies. The unstructured covariance will be used in the modelling of the within-patient errors in the analysis. For APOE4 status subgroup analysis of MMRM, APOE4 factor will not be considered in the model. AUC of Anti-A β antibodies will be used an analysis of covariance (ANCOVA) model with treatment and baseline of Anti-A β antibodies as covariate. Antibody responders will be defined as the subjects with serum antibody titer > response threshold at any visit after baseline. The number and percentage of patients will be tabulated for each treatment group in mITT Population and PP Population at each post treatment scheduled visit. Treatment differences in the proportion antibody responders will be analyzed with the Chisq test. The one-sided 95% confidence interval (CI, right side) from all visits (V1 to V13) for subjects in Arm 3 (placebo group) will be calculated as the threshold of response.

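### The responder rule ignores the subject's own V1 titer, so a high titer that never rises counts as a response, mainly inflating the placebo rate and narrowing the treatment difference

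*Protocol*

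**What the plan says.** The responder rule appears four times, in Protocol 6.1.2 and 9.2.2 and in SAP 4.2 and 5.9, and it is the same each time. Protocol 6.1.2 states it as "Antibody responder is defined as the study subject whose serum antibody titer is greater than the response threshold", counting any post-baseline visit. SAP 5.9 words it as "Antibody responders will be defined as the subjects with serum antibody titer > response threshold at any visit after baseline". The threshold, defined in Protocol 9.2.2 and repeated in the SAP, is a right-sided 95% confidence limit computed from Arm 3 titers pooled over V1 to V13. It is one number for everybody.

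On the denominator, Protocol 6.1.2 says: "Response rate will be calculated as the percent of the number of antibody responders versus the total number of subjects for each arm". On the comparison, SAP 5.9 says: "Treatment differences in the proportion antibody responders will be analyzed with the Chisq test". SAP 4.2 adds a treatment difference with a 90% interval.

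A pre-dose titer exists for every subject. Protocol 6.1.1 schedules anti-Aβ sampling from V1 onward, and at injection visits "blood samples will be collected before the treatment". Baseline titer is used in other analyses: SAP 5.9 lists "study visit, time-by-treatment, APOE4 status, and baseline as a" covariate in the mixed model for change in antibody level, and uses it again in the ANCOVA for AUC.

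**The concern.** In all four statements, baseline serves only to mark which visits count. Nothing requires a rise over V1, requires V1 to be at or below the threshold, or removes subjects who begin above it. Because the threshold is built from placebo titers, some untreated titers can lie above it. A subject who begins there and stays there, flat or slowly falling, meets the definition with no vaccine effect.

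The measure then records the presence of antibody rather than a response to injection, and it is a named primary endpoint. The planned tables might not reveal the problem. SAP 5.9 summarises raw V1 titers but tabulates responders only at post-treatment visits, and anti-Aβ titer is not among the baseline characteristics in Protocol 9.2.1 or SAP 4.1. No planned table shows how many subjects began above the threshold.

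**Working it through.** The plan gives no expected response rate, power or V1 titer for this endpoint, so it has no figure to reproduce.

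**Inputs from the documents:** 15 subjects per arm (Protocol 9.1); 13 sampling visits, 12 of them after baseline (Protocol 6.1.1); hence 15 × 13 = 195 placebo values behind the threshold.

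**Assumptions not in the documents:** log-titers are normal, and V1 titers have the same distribution in all arms. Write the threshold as the untreated mean plus k SD.

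**Step 1. Does anything else in the plan exclude the case?** No. Exclusion criterion 13 bars earlier anti-Aβ immunotherapy, and Phase I participants are excluded, but no criterion limits the V1 titer. The denominator is the whole arm. The chi-square test has no stated baseline adjustment.

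**Step 2. How many would begin above the threshold?** A subject with a constant titer is above it with probability p = 1 − Φ(k). The plan does not say whether the limit applies to individual values or to a mean, so both are shown.

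- Upper limit of individual values: k = 1.645, p = 5.0%. Expected per arm 15 × 0.05 = 0.75. Chance of at least one per arm 1 − 0.95^15 = 53.7%.
- Upper limit of the mean, 15 subject means: k = 1.761/√15 = 0.455, p = 32.5%, or 4.9 of 15.
- Upper limit of the mean, 195 values treated as independent (repeated titers are not): k = 1.645/√195 = 0.118, p = 45.3%, or 6.8 of 15.

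When the threshold is estimated from a simulated placebo arm (5,000 trials, constant titers), the three shares become 7.5%, 33.7% and 46.0%.

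**Step 3. Where do these subjects change a rate?** One subject is 1/15 = 6.7 points. In placebo the full amount applies if the titer stays above. In a UB-311 arm, a subject who begins above and then rises is a true responder and adds nothing false. Let q be the share that begins above and would stay above, and r the share of vaccinated subjects who truly rise past the threshold, independent of starting level:

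- placebo rate = q
- UB-311 rate = r + (1 − r)q
- difference = r + (1 − r)q − q = r(1 − q)

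Taking r = 90% as an illustration:

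| q | Placebo | UB-311 | Difference (true 90%) |
|---|---|---|---|
| 5.0% | 5.0% | 90.5% | 85.5% |
| 32.5% | 32.5% | 93.3% | 60.8% |
| 45.3% | 45.3% | 94.5% | 49.2% |

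The active rate barely moves; the placebo rate and the difference do.

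For false responders among the 30 UB-311 subjects, with 5% starting above and 10% failing to rise: 0.05 × 0.10 = 0.005 per subject, 15 × 0.005 = 0.075 expected per arm, and 1 − 0.995^30 = 14% chance of at least one. If 20% fail to rise, 1 − 0.99^30 = 26%. If all rise, 0%.

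**Step 4. What would a required rise do?** A constant-titer subject could no longer be a responder. With visit-to-visit variation, the size of the rise matters. Simulated apparent response with no vaccine effect and within-subject correlation 0.8:

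| Threshold reading | As written | Any rise | ≥1 SD | ≥2 SD |
|---|---|---|---|---|
| Individual values | 19.4% | 18.4% | 7.1% | 0.2% |
| Mean, 195 values | 73.8% | 68.7% | 23.3% | 0.6% |

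In the first row, 13.2 of the 19.4 points come from subjects below the threshold at V1 who cross it by variation, leaving 19.4 − 13.2 = 6.2 points from subjects who began above. The SD multiples are illustrations; the documents give no assay variability.

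**The case against.** The best defence is the concurrent placebo arm. Pre-existing titers are balanced by randomization on average, the placebo rate is reported, and the expected bias narrows the UB-311 difference, which is conservative. The companion primary measure, change from baseline, would show no rise in a flat subject. Prior anti-Aβ immunotherapy is excluded, so vaccine-induced titers at entry should be absent. If V1 titers cluster well below the threshold, nobody is affected. The trial is exploratory, with no power claim for response rate.

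Most of this stands as a limit on size. It does not repair the definition. The arm-specific rate is itself a primary result, balance on average is unreliable with 15 per arm, and a diluted difference is still a wrong estimate. The change-from-baseline model limits the harm without correcting the response rate.

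A reader might infer that the UB-311 rate would be largely spurious, or that the 54% per arm (1 − 0.95^30 = 79% among 30) is the chance of a falsely scored vaccine recipient. The documents do not support either. Those are chances that someone begins above the threshold; a false score also needs the titer not to rise. Protocol Section 1 reports a 100% response in Phase I against an upper limit on the mean baseline titer. That figure may itself include subjects who began above the limit, so it does not prove a high true response, but it gives no ground for assuming a low one. It also makes the mean-limit reading of the present threshold plausible.

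The simulation shows too that much false response can come from variation over 12 visits. That is a separate weakness of the any-visit rule.

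**Conclusion.** The point holds as a defect of definition: followed exactly, the plan scores a persistently high, non-rising titer as a response on a primary endpoint. Its frequency cannot be known from the documents. Under normal log-titers and a common V1 distribution, about 5% of subjects begin above a 95th-percentile threshold, and 32-45% of constant-titer subjects exceed a limit on the placebo mean. The higher range depends on how the threshold wording is read, which is a separate question.

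The expected effect is an inflated placebo rate (up to 6.7 points per affected subject), a UB-311-minus-placebo difference reduced by the factor 1 − q, and possible chance imbalance at 15 per arm. UB-311 rates are inflated only through subjects who fail to rise. It would also go too far to say that the flaw bites under any threshold: one set above every V1 titer would leave no one affected. This should be corrected, but it does not undermine the change-from-baseline analysis.

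**What to change.** In Protocol 6.1.2 and 9.2.2 and SAP 4.2 and 5.9, define a responder as a subject who, at a post-baseline visit, has a titer above the threshold **and** a rise over his or her own V1 titer of at least a stated margin. Fix the margin before unblinding and set it larger than the assay's between-run variability. Requiring any rise at all is not enough, as Step 4 shows. Do not borrow a conventional fold rise without justification; the documents give no basis for a particular figure. Add one table row giving, by arm, the number of subjects whose V1 titer was above the threshold.

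The cost is small: no new samples or visits, since V1 serum is already drawn before the first injection. The margin must be taken from assay validation data; Protocol 6.1.1 calls the assay validated, but the variability is not given there. The reported response rate may be slightly lower.

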### 6.2 Safety

The study-specific and general safety criteria are described in section 7.1 (Safety Endpoints).

A patient card, including the relevant “24 hour alert system” telephone number, will be provided to every subject who participates in the study.

### 6.3 Efficacy

Efficacy variables are evaluated as secondary endpoints in this study.

#### 6.3.1 Evaluation variables

6.3.1.1 The change from baseline in cognitive, functional, and global assessments through the end of the study

- Cognition: ADAS-Cog and MMSE
- Function: ADCS-ADL

- Global: CDR-SB
- Behavior: NPI

### 6.3.1.2 The change of amyloid burden from baseline to Week 52 and Week 78 in retention of 18F-AV-45

The data will be expressed by mean regional standard uptake value ratio (SUVR).

## 6.3.2 Efficacy assessment methods

### 6.3.2.1 Rating scales

All scales are rated by an independent clinical psychologist and/or study nurse who has to complete the training session specifically designed for this study.

MMSE and CDR/CDR-SB are evaluated at the first screening (S1), and at Weeks 24 (V5), 48 (V9) and 78 (V13). ADAS-Cog, ADCS-ADL, and NPI are evaluated at baseline (V1), and at Weeks 28 (V6), 52 (V10) and 78 (V13).

### 6.3.2.2 18F-AV-45 retention measurement

18F-AV-45 PET is conducted at the second screening (S2), and at Weeks 52 (V10) and 78 (V13) to assess the change in A $\beta$  burden from baseline to Weeks 52 and 78 (see Section 3 of Appendix 1 Imaging Protocol).

In case of scanning failure, re-injection/re-scanning of 18F-AV-45 is allowed. The detailed procedures of 18F-AV-45 PET are described in a separate manual, 18F-AV-45 PET Imaging Manual.

## 6.4 Measures to protect blinding of this trial

This is a double-blind study. In order to protect blinding, study drug will be labelled with individual unique randomization codes. In the event that an adverse effect is considered serious and related to the study drug, and knowing the assignment is essential for treating the subject, the investigator is allowed to call IVRS/IWRS to obtain the treatment code of that individual subject. If the treatment assignment is unblinded, the investigator must notify UNS in writing and document the course of the events in the CRF.

The treatment arm for each subject will be coded so that the subject, investigator, and research staff do not know the arm assignment until the end of the study. Personnel related to analysis, statistics, and report writing will remain blinded before database lock.

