### **3.3 Description of Blinding Methods**

The UB-311 and placebo vials are indistinguishable by appearance. Each treatment box is labeled with a number, which is generated by a computer program from UNS's delegate CRO. Investigators do not have access to the randomization code except under circumstances described in section 6.4.

To maintain the blind during the trial, neither the investigator nor the sponsor will have access to the data that could potentially compromise study blindness during the study.

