Medical and scientific judgment should be exercised in deciding whether expedited reporting is appropriate in other situations, such as important medical events that may not be immediately life threatening or result in death or hospitalization but may jeopardize the subject or may require intervention to prevent one of the other outcomes listed in the definition above.

An adverse event fulfilling any one or more of these criteria should be reported as a serious adverse event, irrespective of the dose of drug given, and even if it is the result of an interaction or drug abuse.

A distinction should be drawn between serious and severe adverse events. The term 'severe' is often used to describe the intensity (severity) of a specific event (as in mild, moderate, or severe myocardial infarction); the event itself, however, may be of relatively minor medical significance (such as severe headache). This is not the same as 'serious,' which is based on subject's event outcome or action criteria usually associated with events that pose a threat to a subject's life or functioning. The seriousness (not severity) serves as a guide for defining regulatory reporting obligations.

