**Activities of Daily Living (ADL):**

\*Instrumental ADL refers to preparing meals, shopping for groceries or clothes, using the telephone, managing money, etc.

\*\*Self care ADL refers to bathing, dressing and undressing, feeding self, using the toilet, taking medications, and not bedridden.

The investigator makes a judgment regarding whether or not the AE is related to study drug, using the definitions below. The investigator is to evaluate any changes in laboratory values and make a determination as to whether or not the change is clinically important and whether or not the changes are related to study drug. However, even if the investigator determines there is no relationship to the study drug, the AE or clinically significant laboratory abnormality must still be recorded in the CRF along with the investigator’s assessment of relationship as follows:

Relationship	Description
Unrelated	The AE must definitely have been caused by the subject’s clinical state, or the study procedure/conditions (i.e. it had no association with the study drug)
Unlikely	The temporal association between the AE and the study drug was such that the study drug was not likely to have any reasonable association with AE.
Possible	The AE followed a reasonable temporal sequence from the time of drug administration, but could have been produced by the subject’s clinical state or the study procedures / conditions.
Probable	The AE followed a reasonable temporal sequence from the time of study drug administration, abated upon discontinuation of the study drug and could not be reasonably explained by the known characteristics of the subject’s clinical state.
Definite	The AE followed a reasonable temporal sequence from the time of study drug administration, abated upon discontinuation of the study drug and reappeared when the study drug is introduced.

It is usually important for the investigators to take information of underlying diseases, concomitant drugs, temporal relationship of the onset of the event to the time of dosing the study medication, and re-challenging outcomes, into account when making a causal relation decision.

It is the investigators' responsibility to follow proactively the outcome of each AE/SAE until resolution or stabilization of the condition or lost of follow-up.

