### **7.7 Follow-up**

The investigator should take all appropriate measures to ensure the safety of the subjects; notably he/she should follow up the outcome of any AEs (clinical signs, laboratory values or other, etc.) until the return to normal or consolidation of the subject's condition.

In case of any SAE, the subject must be followed up until clinical recovery is complete and laboratory results have returned to normal, or until progression has been stabilized. This may imply that follow-up will continue after the subject has left the clinical trial.

In case of any SAE brought to the attention of the investigator at any time after the initiation of clinical trial and considered by him/her to be caused by the study drug with a reasonable possibility, this should be reported to the sponsor or the sponsor's delegate within the time frame beginning from the investigator's knowledge of the event.

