### **7.8 Obligation of the Sponsor**

During the course of the study, the sponsor will report in an expedited manner all SAEs that are both unexpected and at least reasonably related to the study drug to the health authorities, IRBs as appropriate and to the investigators.

In addition, the sponsor may report in an expedited manner all SAEs that are expected and at least reasonably related to the study drug to the authorities, according to local regulations.

The sponsor will report all safety observations made during the conduct of the trial in the clinical study report (CSR).

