### **6. Meningoencephalitis Management by Investigator**

If meningoencephalitis occurs, investigator will treat the subject with standard clinical procedures, such as giving bed rest, avoiding daylight, supplying fluid, and providing medications for pain control including anti-inflammatory, anti-convulsant and anti-emetic drugs. Corticosteroids may be prescribed to reduce tissue swelling or cerebral edema if necessary.

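### The emergency unblinding rule requires a judgment that the event is drug-related, so an event rated Unrelated has no permitted code break even when the assignment is essential to care

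*Protocol*

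**What the plan says.** Protocol section 6.4 states when an investigator may call the IVRS/IWRS for one subject's code: when "an adverse effect is considered serious and related to the study drug, and knowing the assignment is essential for treating the subject". After a break the investigator must notify the sponsor in writing and document the events in the CRF.

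Section 3.3 ties all investigator access to that rule: "Investigators do not have access to the randomization code except under circumstances described in section 6.4". It also keeps both the investigator and the sponsor away from data that could compromise the blind during the study.

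Relatedness is the investigator's judgment on the five-level scale in section 7.6. Unrelated means that "it had no association with the study drug". Unlikely means the timing was such that "the study drug was not likely to have any reasonable association with AE". The other levels are Possible, Probable and Definite. Section 6.4 does not say which levels count as related.

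**The concern.** The cause of an event and the safe treatment of it are separate questions. Section 6.4 accepts that knowing the arm can be essential to treatment, but it also makes access depend on an opinion about cause, formed blind and possibly under time pressure. An investigator who is confident that the vaccine did not cause the event, yet needs to know whether the subject received it, would have to depart from the protocol to find out.

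What is at stake is the care of an individual subject. No estimate, test or error rate in the plan depends on this rule.

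**Working it through.** **Step 1. The rule as a condition.** From 6.4: code break permitted = serious AND related AND essential for treatment. From 3.3: no investigator access otherwise.

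| Serious | Related | Essential | Code break permitted? |
|---|---|---|---|
| yes | yes | yes | yes |
| yes | no | yes | no |
| no | yes | yes | no |
| any | any | no | no |

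The second row is the finding. The third is a parallel gap for non-serious events. It should be small, because section 7.5 counts as serious a medically important event that "may jeopardize the subject or may require intervention to prevent one of the other outcomes listed in the definition above".

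**Step 2. Is there another route?** None was found in the Protocol's sections on randomization (3.4), stopping rules (3.5), withdrawal (4.4), the 24-hour patient card (6.2), safety instructions and adverse event reporting (7.2 to 7.8), the DSMB (7.9) or risk management (7.10). The SAP has no unblinding provision.

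**Step 3. Which causality levels fail the condition?**
- *Unrelated*: fails on any reading.
- *Unlikely*: probably fails, by inference from its definition.
- *Possible*: probably passes. Section 7.7 speaks of an SAE "considered by him/her to be caused by the study drug with a reasonable possibility", and section 7.8 of SAEs "at least reasonably related to the study drug".
- *Probable* and *Definite*: pass. However, 7.6 requires that the event abated on stopping the drug and, for Definite, also that it came back when the drug was given again. That information is seldom available in an emergency, so in practice access may turn on whether Possible counts, which 6.4 leaves unsaid.

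**Step 4. What the fix could cost in the analysis.** If the code is broken before causality is recorded, the causality call is no longer blind. Causality enters the tolerability formula (Protocol 9.4.2; SAP 5.8) and the tables of treatment-emergent events by relationship (Protocol 9.4.5.1; SAP 5.12.2).

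Tolerability = 100% × (A + B1 + C + D) / (A + B1 + B2 + C + D)

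Inputs: 15 subjects per arm (Protocol 9.1) and 7 injections each (Protocol 5.2), so 15 × 7 = 105 doses. Assumption: 14 subjects complete all doses (A = 14 × 7 = 98) and one drops out for an adverse event after k doses.
- Called drug-related: B1 = k, B2 = 7 − k, tolerability = (98 + k)/105.
- Called drug-unrelated: C = k, B2 = 0, tolerability = (98 + k)/(98 + k) = 100%.
- Difference = (7 − k)/105.

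| k | If related | Difference |
|---|---|---|
| 1 | 99/105 = 94.3% | 6/105 = 5.7 points |
| 6 | 104/105 = 99.0% | 1/105 = 1.0 point |
| 7 (drop-out in follow-up) | 105/105 = 100% | 0 |

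If only UB-311 doses are counted in Arm 2 (15 × 5 = 75), the difference is (5 − k)/75: 4/75 = 5.3 points at k = 1 and 0 at k = 5.

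**The case against.** The strongest reply is that the excluded case is nearly empty. Section 7.6 reserves Unrelated for events that were definitely caused by something other than the drug. An investigator with real doubt can choose Possible, which probably opens access. What remains is an event certainly not due to the vaccine whose treatment still depends on it, and the documents describe none. For meningoencephalitis, section 7.10 says the "investigator will treat the subject with standard clinical procedures", with no reference to arm. Dosing can be stopped without the code (4.4). The premise in 6.4 that the assignment may be essential is stated only for serious, related events. A narrow rule also protects the blind in a trial of 15 per arm with rater-scored outcomes.

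Much of this stands, and it limits the severity. The gap is firm for one causality level of five, and no arm-dependent treatment is named. A case can be imagined: section 5.5.2 prohibits heparin and thrombolytic therapy, and 7.2.2 notes that ARIA has been reported with amyloid-lowering therapies. A clinician weighing such treatment for an unrelated event might want to know the arm. The protocol gives no reason for the prohibition, so this shows plausibility only.

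The reply does not cure the rule. The general duties to protect subjects (7.7) and to follow GCP (10.1) grant no access to the code. The protection for the blind comes mainly from requiring that the assignment be essential for treatment, and that requirement would stay.

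A reader might infer that any event not firmly attributed to the vaccine is barred. Sections 7.7 and 7.8 point the other way for Possible.

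**Conclusion.** The point holds as a minor patient-safety matter. Sections 6.4 and 3.3 together leave an event rated Unrelated, and by inference Unlikely, without a permitted code break even when the assignment is essential to the subject's care. The conclusion rests on the wording of the two sections and on the absence of any other route in the Protocol or SAP.

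The case should be rare. The documents give no event rate from which to estimate how many subjects would be affected, so the defect has no numerical size.

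A reader might also infer that the rule threatens the trial's results, or that the 5.7-point figure measures harm from it. Neither is supported. No planned analysis depends on the rule, and the 0 to 5.7 points describe one possible side effect of the remedy, under the assumption of 14 full completers and a single drop-out.

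**What to change.** In section 6.4, and in any matching IVRS/IWRS instruction (none is included in the documents), allow the code break whenever knowing the assignment is essential for the subject's emergency medical care. Require no judgment of relatedness or seriousness. Section 3.3 already refers to 6.4 and needs no separate change. Keep the written notification to the sponsor and the CRF documentation.

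Add one line: record the investigator's blinded causality opinion before the break whenever this does not delay care, and mark in the CRF any causality opinion given afterwards.

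The change costs about two sentences and a check of the system instruction. The downside is possibly a few more single-subject unblindings and an occasional causality call made with the arm known. Recording causality first limits the second.
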